In this study, we will continue to test the efficacy of the device on individuals with stroke in their home environment. Efficacy will be evaluated based on the change in gait coordination as well as other gait and mobility parameters including gait speed, balance, and fall risk. This study will also integrate motion sensor technology in order to obtain real-time data, e.g. gait analysis. We predict that the device will continue to demonstrate changes to interlimb coordination of gait as well as improvement in gait and mobility parameters.

[figure not shown]

Figure 1: Picture of device – note that wheels are designed such that downward force (i.e. from standing) will cause them to rotate and move the shoe backwards, relative to the ground. (bottom) The motion of the device from heel contact until toe off of walking. The device was measured to have a smooth horizontal backward motion of approximately 6-8" (15-20 cm).

1. Background information, description of existing research, and information that is already known

In the United States, nearly 800,000 people suffer a stroke each year, and approximately two-thirds of these individuals survive⁸. Many people suffer from significant and long-lasting motor deficits that require rehabilitation. One such motor deficit that frequently occurs is hemiparesis, or a weakness on one side. Among ischemic stroke survivors over 65 years old, half had some degrees of hemiparesis persisting six months post-stroke.⁹ Lower limb hemiparesis leads to asymmetric walking patterns, called hemiparetic gait.^{10,11} Specific characteristics of hemiparetic gait include asymmetries in temporal (e.g. swing time and double-support time)^{10,12} and spatial (e.g. step length)¹³ measures of interlimb coordination. That is, the timing and placement of the feet are not equal on the two sides.

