The asymmetric nature of hemiparetic gait can have a large impact on functional walking ability. For example, swing phase asymmetry is a significant predictor of hemiparetic walking performance because it strongly correlates with stages of motor recovery, walking speed, and falls.^{10,12} Another measure of temporal asymmetry – double support duration – is similarly correlated with walking speed.¹⁴ In addition, spatial (e.g. step length) asymmetry is associated with decreased propulsive force on the paretic leg,^{13,15} which limits forward motion of the body and reduces gait efficiency^{16,17}. The importance of gait efficiency should not be understated – the elevated energy demands of hemiparetic gait combined with physical deconditioning post-stroke can greatly limit performance of activities of daily living, contributing to poor cardiovascular fitness and metabolic syndrome. In turn, this can increase the risks of a second stroke or cardiovascular event and is associated with increased morbidity and mortality rates.¹⁸ Therefore, improving gait symmetry should be an important goal for therapy, to not only improve functional mobility and reduce injury, but also to enhance general health and well-being post-stroke.

Practicing walking on a split-belt treadmill can correct abnormal interlimb coordination of gait in individuals with hemiparesis following stroke or other central nervous system lesions^{1,2}. Asymmetric gait can manifest as a spatial asymmetry, in which steps taken on one side are longer than those on the other. It can also manifest as a temporal asymmetry, where the timing is uneven on the paretic and non-paretic sides. Temporal asymmetries are often measured as differences in the duration of double support periods, which are the amount of time both feet are simultaneously contacting the ground and are measured separately for the paretic and non-paretic sides. The device is designed to cause changes in both spatial and temporal gait symmetry. We predict that the device would cause the steps on the

side with the device to be larger since individuals would compensate for the backward rolling motion by placing their foot farther forward in stance, thus increasing the distance between the two feet. Similarly, since the stride is longer, it may also shorten the duration of stance relative to the other side. With shortened stance duration, the amount of time spent in double-support at the end of stance would likely decrease as well.

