The goal of this study is to test the efficacy, safety, and feasibility of the iStride™ device to correct gait asymmetry and improve gait parameters including gait speed and balance in individuals with stroke. The study will be structured around subjects walking on the device with their gait recorded and analyzed before and after device usage. The study design is within-subjects where each individual's gait will be compared before, during, and after the treatment period. The study will be conducted on chronic stroke patients in a home-based setting. The treatment will last at least four weeks with an initial visit prior to the start of treatment and several follow-up tests targeted at one month, three months, six months and twelve months post-treatment, in order to measure retention. A subset of the home study patients may be asked to continue treatment with variations in frequency and duration. In addition, several customization factors, specifically to the wheel size, may be tested in order to determine if patients plateau at any point during their rehabilitation. This is important in order to determine the most beneficial prescription for patients while using the device. Additionally, in order to assess muscle activation and response, a subset of these subjects may be asked to visit an alternate clinic site for EMG testing pre and post-treatment.

The home-based treatment will consist of at least twelve treatment sessions performed over a minimum of four weeks with a gait evaluation pretest and initial fitting of the shoe the week before. Gait evaluations will be performed the week before the first treatment and periodically during treatment (no more than once per week). Follow-up tests will be targeted at one week, one, three, six, and twelve months after the final treatment session.

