A study physician or an advanced registered nurse practitioner (ARNP), rehabilitation clinician with knowledge, or subject's physician will perform medical screening or sufficient review of a medical record for the subjects that will participate in the proposed studies. This screen will be used to determine if the potential subjects had one or more cerebral strokes without other medical conditions (e.g., other neurological, orthopedic, etc.) that would affect or explain the subjects' walking or limb movement. Clinical assessments may consist of vision, proprioception, gait analysis and cognitive screening. The 10 Meter Walk Test, Timed Up and Go Test²⁴, Berg Balance Scale, and Functional Gait Assessment tests will be performed to assess changes in subjects' gait velocity, aerobic capacity, and risk of falls, respectively, before, during, and following treatment. Additionally, several psychosocial outcomes will be tested.

To measure gait, Veristride motion sensors will be incorporated. These sensors, along with additional sensors will be used during all treatment sessions creating a complete library of data while using the device during treatment. This data will be analyzed with existing algorithms to measure gait parameters as well as assess changes that may occur as a result of iStride™ device usage. For the subjects in this study who perform treatment with caregiver supervision, these sensors will allow us to verify that the subject completed the treatment as specified. A fit bit device may also be used in this study, in order to track compliance, record telemetry-related data, as well as provide an overall collection of steps per patient.

Our main analysis will be to compare the amount of learning (i.e. deviations from symmetry post-adaptation) to normal baseline symmetry. This will be done using a repeated measures ANOVA to compare baseline gait symmetry at the start of the experiment to post-adaptation at the end of the experiment and on the follow-up assessments. We will quantify the amount of adaptation and the change in gait asymmetry by comparing the magnitude of step length and double support differences during baseline, at the beginning of treatment, during treatment, and after treatment. During a symmetric gait, step lengths on each side are the same; during an asymmetric gait, step lengths are different. These measures are standard accepted measures for measuring gait asymmetries.

4. Sample size

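### Could the device's direct effect while it is worn be counted as learning in the main symmetry analysis?

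*Combined protocol and SAP*

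**What the plan says.** Section 3 (study design) introduces the main analysis with "Our main analysis will be to compare the amount of learning (i.e. deviations from symmetry post-adaptation) to normal baseline symmetry". It then names the method, an ANOVA for repeated measures, whose purpose is given as: "compare baseline gait symmetry at the start of the experiment to post-adaptation at the end of the experiment and on the follow-up assessments". A separate sentence says that the amount of adaptation and the change in asymmetry will be quantified by "comparing the magnitude of step length and double support differences during baseline, at the beginning of treatment, during treatment, and after treatment".

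On measurement, the same section says "Gait evaluations will be performed the week before the first treatment and periodically during treatment (no more than once per week". It places motion sensors in every treatment session, "creating a complete library of data while using the device during treatment". It also describes gait as recorded before and after use of the device, and says the follow-up tests are there to measure retention.

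Section 1 (background) predicts what the worn device does. It expects steps on a "side with the device to be larger since individuals would compensate for the backward rolling motion by placing their foot farther forward in stance", and adds that "the amount of time spent in double-support at the end of stance would likely decrease as well". The Figure 1 caption adds: "The device was measured to have a smooth horizontal backward motion of approximately 6-8" inches, or 15-20 cm.

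Section 4 sets 18 subjects from a pre-treatment to post-treatment t-test with an effect size of 0.68 for step length difference. Section 5 requires gait asymmetry at entry, and Section 2 gives symmetric gait as the aim.

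**The concern.** Two adjoining sentences give two sets of time levels, and one set includes the beginning of treatment and the treatment period. The only sensor use that Section 3 ties to particular occasions is in treatment sessions, on the device. An analyst could therefore fill those two levels with on-device recordings. The device is expected to move step length and double support directly, so those levels would mix its mechanical effect with any learning. An overall time effect could then be significant although unaided walking had not changed, and the trial might report a training effect it had not shown.

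The definition of learning adds to the unease. Equating it with deviation from symmetry suits walkers who start symmetric. These participants must be asymmetric to enter, so a literal reading makes more deviation look like more learning.

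**Working it through.** **1. The plan's own figure.** Section 4 gives d = 0.68 and N = 18 but no alpha or power. Assume a paired t-test, two-sided 5%, 80% power.

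- Normal approximation: n = ((1.960 + 0.842)/0.68)² = 16.97, rounded up to 17.
- Exact noncentral t: n = 19. At n = 18 the power is 77.6%.

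The stated 18 lies between these. The concern does not touch it if both tests are walked without the device.

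**2. The feared case.** Assume no lasting change, sphericity, and an SD of the paired change equal to 1, so the residual variance is 0.5. The level means are (0, s, s, 0) for baseline, beginning, during and after.

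- The grand mean is s/2, so the squared deviations sum to 4 × (s/2)² = s².
- Noncentrality λ = 18 × s²/0.5 = 36s².
- F has 3 and 17 × 3 = 51 degrees of freedom.

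**3. The direction assumption.** Step 2 shifts every participant the same way. The measure is the size of the left-right difference, and Section 3 lets the device foot be chosen for each participant from several gait parameters. A longer step on the device side can therefore widen one participant's difference and narrow another's. The last two columns repeat the model by simulation, with each participant's direction drawn at random (rates good to about a percentage point).

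| Shift s (SD) | λ | All same direction | 75/25 split | 50/50 split |
|---|---|---|---|---|
| 0.25 | 2.25 | 19.9% | about 8% | about 5% |
| 0.5 | 9 | 67.4% | about 19% | about 5% |
| 0.75 | 20.25 | 96.6% | about 34% | 5-6% |

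In every case the baseline-to-after contrast, walked without the device, stays at 5%.

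**4. Which shift is realistic?** The documents do not say. The 15-20 cm in the figure caption is the travel of the shoe, not a change in step length difference, so any conversion to SD units would be invented.

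**5. Which levels are in the test?** Set the sentences side by side:

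- The ANOVA sentence has three kinds of level: baseline, end of experiment, follow-ups.
- The descriptive sentence has four levels, two of them during treatment, and names no test.

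The four-level F in step 2 appears in neither. The levels in the ANOVA sentence fall before treatment starts or after adaptation. The follow-ups serve to measure retention, which is meaningful only with the device off, and Section 3 describes recordings before and after device use. On that reading no on-device level enters the main test, and its error rate is the nominal 5%.

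**6. The wording on learning.** The F test across time levels is the same whatever the change is called. The direction is read from the means, and Section 2 says which direction is benefit: towards symmetry.

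**The case for a change.** The strongest reply is that the protocol never actually states a device condition, even for baseline and follow-up. The on-treatment levels are part of the design, since Section 3 compares gait before, during and after the treatment period. It also says the session recordings will be used to assess changes from device use. A careless analyst could pool everything, and one added sentence would prevent it. Even outside the ANOVA, a paired t-test of an on-device level against baseline with 18 subjects would reject 52% of the time at a shift of 0.5 SD with no learning at all.

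The textual part of this stands: the condition is unstated, and the definition of learning is loose. The consequence does not. An on-device level compared with baseline shows how gait responds while the device is worn, which is a fair thing to describe under adaptation. It becomes misleading only if relabelled as retained change, and the plan ties its main comparison to the post-adaptation and follow-up levels.

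It is also argued that the main outcome should be narrowed to step length difference at the one-week test, with double support made secondary. That is a debatable trade-off. Section 4 does not define post-treatment as the one-week test, that test appears in only one of Section 3's two follow-up lists (a clerical slip), and a single early time point has costs of its own.

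**Conclusion.** No change is needed. The observation about the text is correct, but it concerns missing detail in a descriptive sentence, and an analyst would fill it sensibly by keeping on-device recordings as a description of adaptation. The repeated measures ANOVA, on the levels its own sentence names, gives a usable main test at 5%, and the powered pre-post contrast is unaffected.

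The rates of 20%, 67% and 97% are arithmetically right. They are the upper end of a range that runs down to about 5%, depending on whether participants shift in the same direction, and they apply only to a four-level test that the plan does not set out.

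This conclusion rests on two readings: that baseline, end-of-experiment and follow-up tests are walked without the device, which Section 3 implies but does not state, and that the ANOVA uses only the levels in its own sentence. If on-device values were in fact put into the main test, the concern would revive, with a size that the documents do not allow anyone to estimate.

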Preliminary studies with three healthy test subjects showed statistical data that indicated that the minimum number of subjects for this study is 18.⁴ We powered the t-test between pre-treatment and post-treatment data. We calculated an effect size of 0.68 for step length difference, resulting in an estimated sample size of 18 subjects. The preliminary test with healthy subjects was approved under the Einstein Healthcare Network IRB HN4365, and other preliminary tests with healthy subjects were conducted under USF IRB Pro00001858.

We have no reason to think that women and men will differ in their abilities on any of these tasks. As such, we expect to enroll approximately the same number of men and women.

5. Inclusion and exclusion criteria

We will recruit individuals with stroke for this study. If eligible and willing, individuals that participated in our previous home study may be allowed continued participation. Since the focus of this project is to ultimately use this device to help stroke survivors, we will recruit both young adults and older adults.

Inclusion criteria includes:

- 1) Age 21-80
- 2) One or more cerebral strokes, but all strokes on same side
- 3) Stroke occurred at least 6 months prior to enrollment
- 4) Gait asymmetry, but able to walk independently with or without a cane
- 5) Not currently receiving physical therapy
- 6) No evidence of severe cognitive impairment that would interfere with understanding the instructions
- 7) No evidence of one-sided neglect, affecting ambulation
- 8) At least 25 feet of walking space (does not need to be a straight line)
- 9) Weight does not exceed 275lbs

Exclusion criteria includes:

- 1) Uncontrolled seizures
- 2) Metal implants (stents, clips, pacemaker)
- 3) Pregnancy
- 4) History of a neurological disorder other than stroke (Parkinson's, MS)
- 5) Chronic Obstructive Pulmonary Disease
- 6) Uncontrolled blood pressure
- 7) Head injury in the past 90 days
- 8) Myocardial infarction within the last 180 days
- 9) Cannot rely on a rolling walker for ambulation
- 10) Severe Ataxia
- 11) Previously diagnosed vestibular ear issues

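### The 18 subjects were sized for one pre-post t-test on step length, but the main analysis is a repeated measures ANOVA on two measures with no primary contrast, sphericity handling or multiplicity rule

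*Combined protocol and SAP*

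**What the plan says.** Section 4 (Sample size) bases the number of subjects on one comparison: "We powered the t-test between pre-treatment and post-treatment data". It continues: "We calculated an effect size of 0.68 for step length difference, resulting in an estimated sample size of 18 subjects". The effect size comes from three healthy volunteers. Alpha, sidedness and target power are not given.

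Section 3 (study design) describes the main analysis differently: "This will be done using a repeated measures ANOVA to compare baseline gait symmetry at the start of the experiment" with the end of the experiment and the follow-up assessments. The amount of change is to be quantified by "comparing the magnitude of step length and double support differences" at baseline, at the start of treatment, during treatment and afterwards. The same section sets one baseline evaluation, an open number of evaluations during treatment (at most weekly), and follow-up at one week and at one, three, six and twelve months.

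A separate paragraph of section 3 lists four functional tests and adds: "Additionally, several psychosocial outcomes will be tested". These stand outside what the plan calls its main analysis.

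The plan nowhere names a primary measure, visit or contrast, a testing order, a multiplicity adjustment or a sphericity correction.

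**The concern.** A sample size supports a conclusion only if the powered test is the one that decides the result. Here the powered test is one contrast on one measure, while the stated main analysis is an omnibus test over several visits for each of two measures. An omnibus test asks whether any visit differs from any other. It does not by itself answer whether asymmetry fell from before to after treatment.

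Two things are at stake. First, the power implied by 18 does not carry over automatically to the planned analysis. Second, success is undefined: with two measures and several visits, a favourable result on either measure could be presented as the finding, and nothing fixes the overall error rate. Visits spaced from one week to twelve months also make unequal correlations likely. A repeated measures ANOVA is sensitive to that unless a correction is specified.

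**Working it through.** **Inputs from the plan.** Effect size d = 0.68 and n = 18 (section 4); two measures, baseline and five follow-up visits (section 3). The t-test is not called paired, but "The study design is within-subjects", and a two-sample test would need 34 per arm, so I read it as paired.

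**Assumed, because not stated.** Two-sided alpha 0.05, power 0.80, and all correlations.

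**Step 1: reproduce 18.** Normal approximation: n = ((1.960 + 0.842)/0.68)² = 16.97, so 17. Exact noncentral t: 19. The stated 18 lies between them. One-sided 5% with 85% power (16 normal, 17 exact) or 90% power (19 normal, 20 exact) comes equally close, so the missing alpha and power cannot be recovered from n.

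**Step 2: power of the powered test at n = 18.** Noncentrality = 0.68 × √18 = 2.885 on 17 df. Power is 77.6% two-sided at 5% (86.9% one-sided).

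**Step 3: two measures.**
- Two omnibus tests at 5% each, if independent: 1 − 0.95² = 9.75%, about 9.8%. Positive correlation between the measures would lower this.
- Splitting alpha to hold 5% overall: 0.05/2 = 0.025. The pre-post t-test then has 66.6% power at n = 18, and 24 subjects are needed for 80%. This assumes d = 0.68 for the measure tested; the plan gives no effect size for double support.

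**Step 4: the omnibus ANOVA with equal correlations.** Scale the SD of the paired difference to 1, so that σ²(1 − ρ) = 0.5. Take six time points and an effect sustained at every visit after baseline. Then Σ(μ − mean)² = 0.68² × 5/6 = 0.3853 and λ = 18 × 0.3853/0.5 = 13.87. With 5 and 85 df, power is about 81%. Under this structure the ANOVA loses nothing against the t-test.

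**Step 5: other correlation structures (illustration only).** Simulation with n = 18, evaluations at weeks 0, 6, 9, 18, 31 and 57, a sustained effect, and the baseline to first post-treatment contrast fixed at d = 0.68:

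| Assumed correlation | Uncorrected ANOVA power | Uncorrected type I error |
|---|---|---|
| Equal across visits | about 81% | about 5% |
| 60% stable, 20% decaying, 20% independent visit noise | 69–71% | 5.0–5.8% |
| Pure decay, 0.90 per week | 54% | 6.4% |
| Pure decay, 0.95 per week | 40% | 7.5% |
| Pure decay, 0.98 per week | 30% | 9.0% |

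The paired t-test stays at 77–78% throughout. A Greenhouse-Geisser correction keeps type I error below 5% in every row, but under pure decay power falls to 43%, 27% and 17%.

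**The case against.** The pre-post contrast is contained in the ANOVA, and sizing a study on a key contrast is ordinary practice. The study is within-subjects, covers safety and feasibility as well as efficacy, and is described as groundwork for later studies. Much of this stands: the arithmetic behind 18 is sound, and an ANOVA is not in itself a poor choice. What does not stand is the implied link. The plan never says that the pre-post contrast decides the result, and it never calls the analysis exploratory.

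Three stronger readings are tempting and are not supported:

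- *The ANOVA has far less power than the t-test.* That needs correlation that decays with no independent visit-to-visit noise. At 0.90 per week the baseline to twelve-month correlation would be 0.90^57, about 0.002, so a chronic patient's asymmetry would be unrelated to its own starting value. With a stable component and visit noise, power is about 70%.
- *The ANOVA's error rate exceeds 5%.* That holds only with unequal correlations and no correction. The plan does not say that the test is uncorrected; it is silent.
- *The false-positive risk is about one in three.* Unadjusted tests of two measures at five follow-ups would give 32–34% under a flat correlation of 0.8, but section 3 specifies an ANOVA, not those pairwise tests. The functional and psychosocial outcomes should not be counted in the main analysis either.

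**Conclusion.** The point holds: the test that set n = 18 is not the planned main analysis, and the plan states no primary contrast and no control of error across the two measures. What can be said without assuming correlations between visits is modest but real: about 9.8% family-wise error for two independent omnibus tests at 5%, or 66.6% instead of 77.6% power for the pre-post test if alpha is split. Both rest on an assumed two-sided 5% level, and the power figures also on a paired test with d = 0.68. The ANOVA's own power (about 30% to 81%) and uncorrected error (about 5% to 9%) depend on unstated correlations. They show why the structure must be addressed; they do not estimate what this trial will deliver.

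**What to change.** Amend sections 3 and 4 together.

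- **Primary test.** Step-length asymmetry, baseline against the first post-treatment evaluation, by paired t-test at two-sided 5%. Name the visit explicitly, because section 3 gives two follow-up lists and only one includes the one-week visit.
- **Power.** State alpha, sidedness and the effect size, and give power at n = 18 as about 78%.
- **Next in order.** Test double support at the same visit, then the follow-up visits, in a fixed sequence at 5%, stopping at the first non-significant result. Apply a Greenhouse-Geisser correction to any omnibus ANOVA that is kept.
- **Other outcomes.** Label the functional tests and psychosocial outcomes as secondary, with Holm's adjustment, or as exploratory.

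This changes wording only: no additional subjects, visits or measurements. The cost is that secondary results face a stricter threshold, and a failure early in the sequence leaves later results descriptive.

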During the treatment, the licensed physical therapist will determine, based on eligibility, if the participant can use the device with their caregiver providing supervision (without the presence of the physical therapist each session). To promote continued safety, the caregiver would be required to participate in a treatment session on the device and would need to demonstrate adequate knowledge of device usage as well as how to walk with the participant safely. The therapist would have weekly or monthly follow-up visits to monitor continued safety, protocol adherence, and progress. Additionally, the participant may communicate some or all sessions with a licensed therapist via telemedicine video conferencing using the 9zest digital health rehab platform (<https://9zest.com>). This communication may be used to enhance communication with the physical therapist. This telemedicine modality is verified HIPPA compliant.

A cross over component may also be employed, in which an equal number of treatment sessions will be duplicated without the device, before or after the device treatment. In a study of this type, the patients will have an equal number of sessions of treatment without the device, in the setting and in the way the treatment will occur with the device. (e.g. at home with caregiver supervision and a physical therapist intermittently following-up).

The treatment sessions will consist of approximately 30 minutes of treatment on the device. The treatment duration will be divided into up to six shorter bouts of walking to allow rest breaks between walking sessions, if needed. Additional breaks will be given as needed upon subject request. Based on the pre-treatment gait analysis, we will evaluate all parameters (such as walking speed, double limb support, stance time, etc) and make a decision to maximize their recovery in regard to which foot the device will be placed on. The device will encourage them to take larger steps with that foot. The total treatment sessions will be no longer than one hour.

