If a patient presents with significant ataxia or previously diagnosed vestibular ear issues, they are excluded from participation in the portions of this trial where the device is used without a therapist present. Patients with previously diagnosed ataxia or vestibular conditions may still participate in the part of the study where a licensed therapist is present at all times with the patient, after clearance by a physician and the clinical therapist who will interact with the patient.

The expected results of the research

This study will enhance rehabilitation methods used for lower limb rehabilitation, which is currently administered with a split-belt treadmill and other traditional methods. This method aims to improve upon existing methods and to also eventually enable a home-based solution. The study results will be submitted to rehabilitation, neuroscience, and engineering publications for dissemination to researchers and clinicians who are interested in using and expanding this method.

6. Roles of study staff

This study is being conducted in several geographic areas for home-based testing. The home-based study will be conducted by [name], DPT, [name], DPT, [name] PhD and [name]. Specific roles include:

[name] and [name] will be responsible for overseeing and training new study staff for the home-based study

[name] will provide medical oversight for the home-based study

[name] and [name] will be responsible for data analysis

Sites

The study will be conducted in the home setting of each subject. Subjects will be recruited in the following geographical areas: Charlotte, NC; Greenville, SC; Atlanta, GA; and Houston, TX. [name] is the central place for study personnel, computer, and engineering.

7. Potential risks to the subjects

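### Does the 25-foot walking-space criterion undermine the 10 Meter Walk Test in a home-based study?

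*Combined protocol and SAP*

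**What the plan says.** Section 5, inclusion criterion 8, requires "At least 25 feet of walking space (does not need to be a straight line". It does not say what the space is for.

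Section 3 lists "The 10 Meter Walk Test" first among four functional tests, used to follow "gait velocity, aerobic capacity, and risk of falls, respectively, before, during, and following treatment". On timing, the same section says "Gait evaluations will be performed the week before the first treatment and periodically during treatment (no more than once per week", with follow-up tests at one week and at one, three, six and twelve months. On treatment walking it says "The treatment duration will be divided into up to six shorter bouts of walking to allow rest breaks between walking sessions, if needed".

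On setting, Section 6 says "This study is being conducted in several geographic areas for home-based testing", and under Sites "The study will be conducted in the home setting of each subject". The only other testing location is in Section 3: "a subset of these subjects may be asked to visit an alternate clinic site for EMG testing pre and post-treatment".

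No section gives the place, timed distance, straightness or run-up for the walk test, or requires the same course at each visit. Section 3 is equally silent on how the other three named tests (Timed Up and Go, Berg Balance Scale, Functional Gait Assessment) are administered.

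**The concern.** Set side by side, the criterion and the test look incompatible. A home can qualify with less length than the test needs, and with no straight run at all, yet testing is described as home-based. In such a home the test would need a turn, a shorter distance or another place.

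Gait speed is not incidental. Section 2 names it in the objective, and Section 8 includes it in the hypothesis. The comparison is within subject, so anything that differs between visits enters the estimated change directly. There is one baseline and five follow-ups, which makes six occasions. Weekly tests during a four-week treatment would make ten, if every gait evaluation included the walk test, which the plan does not say. A course that moved from a hallway with a turn to a straight pavement could pass for improvement, and the reverse could hide it.

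**Working it through.** The plan states no expected change in gait speed, so there is no figure of its own to reproduce. The check has four steps.

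**1. Lengths** (Section 5, criterion 8; Section 3, test name).
- 25 ft × 0.3048 = 7.62 m.
- 10 m / 0.3048 = 32.81 ft.
- Shortfall: 10 − 7.62 = 2.38 m, or 32.81 − 25 = 7.81 ft. The floor is 76.2% of the nominal test length, before any run-up.

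The mismatch in length is real.

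**2. Is the space tied to the test?** Criterion 8 mentions no test. Accepting a space that is not straight makes little sense for a timed straight walk. It suits about 30 minutes of treatment walking split into up to six bouts. Section 6 says where the study takes place, not that a timed walk must stay inside the qualifying space. A corridor or pavement at the home would fit the wording. Using the criterion 8 space for the test is therefore an inference.

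**3. If the inference were right, how large could the effect be?** Let measured speed = d / (d/v + t), where d is the distance, v the true speed and t the time lost to one turn. The speeds (0.60 rising to 0.70 m/s, a true change of 0.10) and the values of t are assumptions. With d = 10 m:

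| t (s) | at 0.60 | at 0.70 | change, turn at both visits | turn at baseline only | turn at later visit only |
|---|---|---|---|---|---|
| 1 | 0.5660 | 0.6542 | 0.088 (12% lost) | 0.134 | 0.054 |
| 2 | 0.5357 | 0.6140 | 0.078 (22% lost) | 0.164 | 0.014 |
| 3 | 0.5085 | 0.5785 | 0.070 (30% lost) | 0.192 | −0.021 |

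The losses in the fourth column hold only if t is the same at both visits. Balance is expected to improve (Section 8), so turning may become quicker:
- t falls from 2 s to 1 s: 0.654 − 0.536 = 0.118.
- t falls from 3 s to 2 s: 0.614 − 0.508 = 0.106.

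Both exceed the true 0.10, so a constant turning course need not work against the device. The last two columns need the same participant to turn at one visit and not at the other, which no section suggests would happen.

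**4. A shorter straight walk, recorded at its true length.** Assume a 1 s start/stop cost.
- 10 m at both visits: 0.6542 − 0.5660 = 0.0882.
- 7.62 m at both visits: 0.6411 − 0.5562 = 0.0849.
- 10 m then 7.62 m: 0.6411 − 0.5660 = 0.0751, a shift of −0.013 from 0.0882.
- 7.62 m then 10 m: 0.6542 − 0.5562 = 0.0980, a shift of +0.010.

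The obvious workaround for a short home, walking a shorter straight line and recording it, therefore costs little.

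**The case for a change.** The strongest case for a change does not depend on whose space criterion 8 describes. Even if the 25 ft is only for treatment, the walk test has no stated course, and nothing keeps the course the same from the pretest to twelve months. In a within-subject comparison of about 18 people, a few participants tested on different courses could matter. One line recording a course at the pretest would cost almost nothing.

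Part of this stands. The course is unwritten, and using one course per participant is good practice that belongs in the testing instructions. What does not stand is the step from there to a defect in the plan. The large distortions need three things that the documents do not supply: a test held in the qualifying space, a home near the 25 ft floor, and a turn or a change of course. Section 3 gives no administration detail for any of its four named tests, so this is the document's general level of detail rather than a conflict created by criterion 8.

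Nor would a one-line rule settle the case that prompted the worry. Falling back on a shorter straight distance presumes that a straight run exists, and criterion 8 guarantees none. A complete rule would need a minimum distance and a provision for homes that cannot meet it.

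Section 3 also uses motion sensors to measure gait and lists walking speed among the parameters of the pre-treatment gait analysis. The plan does not say that this replaces the walk test, but the timed walk may not be the only information on speed.

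**Conclusion.** No change to the plan follows. The lengths differ by 7.8 ft, but the plan does not require the 10 Meter Walk Test to be done in the criterion 8 space, so no contradiction is shown. The gap is a missing detail of test administration. That it would be filled sensibly assumes that the licensed physical therapists who screen and follow participants also run the test, and that they use a straight course and keep to it. The documents do not name the tester, but the assumption fits the therapists' role in Section 3.

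The possible effect on gait speed is bounded only by assumption. For a true gain of 0.10 m/s, a turn at both visits gives 0.070 to 0.088 with a fixed cost of 1 to 3 s, and 0.106 to 0.118 if the turn quickens by 1 s from 3 s or 2 s. Direction is not established, and the number of homes near the floor is unknown, so there is no trial-level figure. The main analysis concerns step-length and double-support symmetry (Section 3), and the sample size of 18 rests on step-length difference (Section 4). Neither is affected.
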